Notes: Since the study protocol was written, a new evaluation of the UK stop smoking services was published [12]. The validated one-year quit rate has declined to 8%. This comprised general practice and pharmacy services with quit rates of 5% and specialist support with quit rates of 10% for individual and 12% for group support. The decline is probably due to a 'hardening' of treatment population, e.g. the services see an increasing number of re-attenders, people with serious health issues etc. Using a quit rate of 10% in the UC arm that provides multi-contact support, and 17% in the EC arm (RR=1.70) the study sample size still provides 86% power to detect such a difference with a two-tail test of proportions.

Assuming the true percentage in both arms is 10%, the 95% confidence interval for the difference in proportions will have width of +/-4% around the observed difference.

If the difference in proportions is non-significant, we will undertake a non-inferiority analysis, using a two-sided confidence interval of the difference in the abstinence percentages between the two arms. Assuming that the true percentages are 10% in the control arm and 12% in the intervention arm, our sample size of 886 will provide 88% power to exclude a difference in favour of the standard group of 4% or more.

Data collection

Baseline

The following variables were collected at baseline:

- **Demographics:** includes age, sex, marital status, ethnicity, employment, level of education, eligibility for free prescriptions,
- **Smoking measures:** Fagerstrom Test for Cigarette Dependence (FTCD) [13], previous stop smoking product use, age first started smoking and whether partner/spouse smokes. Mood and Physical Symptoms Scale (MPSS) [14], carbon monoxide reading
- **Current Health and Medications**
- **Health problems checklist**

The following validated questionnaires are also administered at baseline:

- EQ-5D
- Smoking Cessation and Health Service Use Questionnaire

Follow up

The following variables were collected during follow-up visits:

- Current smoking behaviour
- Mood and Physical Symptoms Scale (MPSS) – 1 and 4 weeks post quit only
- Carbon monoxide reading
- Allocated product use, helpfulness, taste and satisfaction ratings (1 and 4 weeks post quit only), purchase and reasons for stopping (where applicable)
- Non-allocated product use and purchase
- Current health and medications
- Health problems checklist

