***See appendix 3 for how data for each outcome was collected**

Differences in tobacco withdrawal symptoms at 1 and 4 weeks.

Between-group differences in urges to smoke, and changes (from baseline) in tobacco withdrawal symptoms will be examined using ANOVA, in both the whole sample, and abstainers only sample.

Treatment ratings (e.g. satisfaction, taste, helpfulness, reasons for stopping product use)

Differences in mean ratings of treatment effects (product helpfulness, taste, satisfaction and reasons for stopping product use) between groups will be examined using ANOVA (or non-parametric tests where normality cannot be assumed) at 1 and 4 weeks post quit with adjustments where needed for normal distribution. NB. Where 2 NRT products were used and rated, the average rating of the two will be taken.

Adverse reactions (ARs)

The frequency of participants reporting each AR (nausea, sleep disturbance or throat/mouth irritation) at least once will be compared between arms using Chi squared test. The MedDRA coding system will be used.

Changes in respiratory problems

Frequency of respiratory problems at baseline and 12 month follow up will be compared between arms using Chi-squared test.

Cost-efficacy of the interventions.

The economic evaluation is conducted alongside the TEC trial by way of a cost-effectiveness analysis. Following NICE guidance, the analysis will be performed from the National Health Service (NHS) and Personal Social Services (PSS) perspective to reflect NHS England decision-making framework [16]. The analysis from a wider perspective will also be conducted to explore the possible societal impact of the intervention. All costs will be presented in 2015/16 Sterling Pounds (£). The objectives of the analysis are:

1. To assess cost-effectiveness of EC over and above UC at 12-month follow-up (primary outcome);
2. To estimate potential long term cost-effectiveness of the intervention.

These objectives will be achieved by combining data collected within the trial and existing models.

Costs estimation

Intervention cost

The intervention consists of six weekly sessions of standard SSS behavioural support for both arms, a starter kit of e-cigarette for the EC arm and supplies of NRT for the UC arm.

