As the primary outcome will be 12-month sustained, biochemically validated abstinence, a cost-effectiveness analysis will be performed at this time point. The costs will include intervention cost, smoking cessation services cost after intervention period and health resources use cost that has occurred during the 12-month period. The difference in costs between arms will be controlled for health resources use at baseline, age, sex, study site, entitlement of free prescriptions, ethnicity and baseline FTCD. The quality adjusted life years (QALYs) will be calculated during the same time period. The difference in QALYs between arms will be controlled for utility value at baseline, age, sex, study site, entitlement of free prescriptions, ethnicity and baseline FTCD. Combining both, an incremental cost-effectiveness ratio (ICER) of cost per QALY will be calculated to assess the cost-effectiveness of the intervention, comparing with the standard care. The ICER will then be compared with the national willingness-to-pay threshold of £20,000-£30,000 per QALY gained [16].

Uncertainty assessment

The uncertainty around the decision to adopt the intervention will be assessed through a non-parametric bootstrap re-sampling technique. Bootstrapping has been proposed as an efficient approach for calculating the confidence limits for the ICER as its validity does not depend on any specific form of underlying distribution [23-26]. A cost effectiveness acceptability curve (CEAC) will be plotted based on the outcomes of the 5000 bootstrap iterations [27].

A separate sensitivity analysis will be carried out to examine the impact of the assumption of LOR equating dispense on the intervention costs. This will be undertaken by using the actual quantities used reported by the participants as the cost base of the NRT costs. A set of weighted average cost per unit of the NRT products will be extracted from Prescription Cost Analysis [17] with the same approach as in the base case analysis. These unit costs will then be multiplied by the quantities reported of corresponding NRT products.

Given that the current practice for smoking cessation does not provide prescription of EC while allows prescription of pharmacotherapies, a separate analysis will be carried out, including participants' out-of-pocket money for EC and pharmacotherapies, to examine the possible cost-shift from NHS to smokers.

Handling missing data

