7-day point prevalence at 52 weeks post TQD, N (%)						

Table 6 – Change in respiratory symptoms

	NRT (N=)		EC (N=)		P-value	Odds Ratio (95% CI)
	Baseline N (%)	12 months N (%)	Baseline N (%)	12 months N (%)		
Shortness of breath						
Wheezing						
Cough						
Phlegm						

Table 7– Percentage participants reporting an adverse reaction at least once

% (N) reporting Adverse Reaction	EC	NRT	P-value
Nausea			
Sleep disturbances			
Throat/mouth irritation			

Table 8 – Differences in urges to smoke at 1 and 4 weeks post quit (abstainers only)

Symptom	1 week post quit		P-value	Mean difference (95% CI)	4 weeks post quit		P-value	Mean difference (95% CI)
	EC	NRT			EC	NRT		
Frequency of urge to smoke – mean (SD)								
Strength of urge to smoke – mean (SD)								
Composite urge score – mean (SD)								

Table 9 – Differences in urges to smoke at 1 and 4 weeks post quit (whole sample)

Symptom	1 week post quit		P-value	Mean difference (95% CI)	4 weeks post quit		P-value	Mean difference (95% CI)
	EC	NRT			EC	NRT		
Frequency of urge to smoke – mean (SD)								
Strength of urge to smoke – mean (SD)								
Composite urge score – mean (SD)								

Table 10 – Change in withdrawal symptoms between baseline and 4-weeks post TQD (abstainers only)

Symptom	NRT (n=)	EC (n=)	P-value	Mean difference, (95% CI)
Depressed – mean (SD)				
Irritable – mean (SD)				
Restless – mean (SD)				
Hungry – mean (SD)				
Poor concentration – mean (SD)				
Composite MPSS score – mean (SD)				

Table 11 – Change in withdrawal symptoms between baseline and 4-weeks post TQD (whole sample)

Symptom	NRT (n=)	EC (n=)	P-value	Mean difference (95% CI)
Depressed – mean (SD)				
Irritable – mean (SD)				
Restless – mean (SD)				
Hungry – mean (SD)				
Poor concentration – mean (SD)				
Composite MPSS score – mean (SD)				

Health economics tables

Table 12: Breakdown of intervention cost (mean [S.D.])

Cost item	NRT (n=xxx)	EC (n=xxx)
Behavioural support sessions		
NRT/EC supplies		
Information sheets		
Total		

Table 13: Unit cost

Services	Unit cost	Sources
Smoking cessation help		
GP		
NHS SSS		
NHS Smoking Helpline service		
Pharmacotherapies		
Patch		
Gum		
Microtab		
Inhaler		
Lozenge		
Spray		
Mouthstrip		
Varenicline		
Bupropion		
Health resources use		
A & E		
Outpatient		
Inpatient		
Day case		
Emergency ambulance		

GP (in office)		
Practice nurse (in office)		
GP (home visit)		
Practice nurse (home visit)		
Prescription		

Table 14: Usage and mean cost of services (mean [S.D.]

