2. A little of the time
3. Some of the time
4. A lot of the time
5. Almost all of the time
6. All of the time

Q7. How strong have these urges been?

1. No urges
2. Slight
3. Moderate
4. Strong
5. Very strong
6. Extremely strong

Definition: Changes in withdrawal symptoms between baseline and 4 weeks on following scale: not at all, slightly, somewhat, very, extremely.

Data source: Q+1 and Q+4 Post Quit CRF,

Q5. For each of the following (depressed, hungry, irritable, poor concentration, restless) rate how you have been feeling over the past week:

1. Not at all
2. Slightly
3. Somewhat
4. Very
5. Extremely

9. Treatment ratings

Definition: Ratings of helpfulness on the following scale: not at all, slightly, somewhat, very, extremely

Data source: Q+1 and Q+4 post quit CRFs

Q8c. Since your last visit/contact how helpful did you find your allocated product(s) in keeping you away from normal cigarettes?

1. Not at all
2. Slightly
3. Somewhat
4. Very
5. Extremely

Definition: Ratings of taste on the following scale: much worse than normal cigarettes, a little worse than normal cigarettes, the same as normal cigarettes, a little better than normal cigarettes, much better than normal cigarettes

Data source: Q+1 and Q+4 post quit CRFs

Q10. How good did it taste?

1. much worse than normal cigarettes
2. a little worse than normal cigarettes
3. the same as normal cigarettes
4. a little better than normal cigarettes
5. much better than normal cigarettes

Definition: Ratings of satisfaction on the following scale: much worse than normal cigarettes, a little worse than normal cigarettes, the same as normal cigarettes, a little better than normal cigarettes, much better than normal cigarettes

Data source: Q+1 and Q+4 post quit CRFs

Q11. How satisfying was it?

1. Much less than normal cigarettes
2. A little less than normal cigarettes
3. The same as normal cigarettes
4. A little more than normal cigarettes
5. Much more than normal cigarettes

10. Adverse reactions (AR) **Definition:** % (N) reporting 'Yes' to adverse reaction on at least one post quit session.

Data source: Health Problems CRF checklist at all post quit sessions (specifically nausea, sleep disturbance and throat/mouth irritation questions).

11. Change in respiratory problems **Definition:** Participants are defined as experiencing the health problem if they responding 'Yes' to it and the given time point.

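### Withdrawal and respiratory outcomes make less use of the collected baseline values than they could, and Table 6 does not fix which respiratory contrast it reports

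*SAP*

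**What the plan says.** **Withdrawal.** The SAP section on withdrawal symptoms reads: "Between-group differences in urges to smoke, and changes (from baseline) in tobacco withdrawal symptoms will be examined using ANOVA". This is done in the whole sample and in abstainers only. Appendix 3, item 8, describes the outcome as "Changes in withdrawal symptoms between baseline and 4 weeks on following scale: not at all, slightly, somewhat, very, extremely". Tables 10 and 11 show change to 4 weeks, with one P-value and one mean difference per symptom. The baseline data list includes "Mood and Physical Symptoms Scale (MPSS) [14], carbon monoxide reading", so a baseline withdrawal score exists. No baseline covariate is named.

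**Urges.** Tables 8 and 9 compare urge frequency and strength as week 1 and week 4 scores. Appendix 3 gives only the Q+1 and Q+4 forms as their source.

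**Respiratory problems.** Under the heading on changes in respiratory problems: "Frequency of respiratory problems at baseline and 12 month follow up will be compared between arms using Chi-squared test". Appendix 3, item 11, defines the outcome as status at one time: "Participants are defined as experiencing the health problem if they responding 'Yes' to it and the given time point". The data source is the checklist at baseline and Q+52. The table shell is "Table 6 – Change in respiratory symptoms". It has baseline and 12-month N (%) for each arm, then a single P-value and a single odds ratio per symptom.

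**Elsewhere.** The base-case economic analysis does adjust: "The difference in QALYs between arms will be controlled for utility value at baseline". Costs are likewise adjusted for baseline resource use. The adjusted model for the primary outcome is a log-link binomial regression with a site term.

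**The concern.** The two outcomes raise different issues.

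For withdrawal, subtracting the baseline score fixes its coefficient at 1 instead of letting the data estimate it. That costs precision unless the true regression slope happens to be 1. A chance baseline difference between arms is then over- or under-corrected.

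For respiratory symptoms, the section heading and table title promise change, but the outcome is status at a time point and no new-onset, resolved or within-person category is defined. The single P-value and odds ratio in Table 6 could be filled from the 12-month comparison, from some comparison of changes, or from an adjusted model. That choice should not be left until the data are seen. If the 12-month comparison is used under a title that says change, a difference already present at entry could be misread as an effect on change.

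At stake are the precision of one listed secondary outcome and the interpretation of one additional safety-type comparison.

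**Working it through.** **The plan's own figure.** The SAP states no power or precision for these outcomes. Its nearest design figure is 886 (443 per arm) for the primary outcome. With continuity correction, 14% v 21% at power 0.75 and two-sided alpha 0.05 gives 437 per arm (874 in total), within 3% of the stated figure. At 443 per arm, power for 10% v 17% is 0.863, against the stated 86%. The design figure reproduces but does not bear on this point.

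**Withdrawal: general result.** Let s1 and s2 be the baseline and follow-up SDs and rho their correlation. Per participant, in large samples:

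- change score: s1² + s2² − 2·rho·s1·s2
- ANCOVA: s2²·(1 − rho²)
- difference: s1² − 2·rho·s1·s2 + rho²·s2² = (s1 − rho·s2)²

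The difference is a square, so ANCOVA is never the less precise of the two. They tie only when rho·s2 = s1.

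**Equal SDs (assumed).** The ratio of ANCOVA to change-score variance becomes (1 − rho²) / [2(1 − rho)] = (1 + rho)/2. The correlations are assumed, because the SAP gives none. Effective N is 886 × ratio and supposes that everyone has both measurements. The last column is the power of the change-score analysis where ANCOVA has 80%: Φ(2.80·√ratio − 1.96).

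| rho | ratio | effective N of 886 | power |
|---|---|---|---|
| 0.2 | 0.60 | 532 | 58% |
| 0.3 | 0.65 | 576 | 62% |
| 0.5 | 0.75 | 664 | 68% |
| 0.7 | 0.85 | 753 | 73% |
| 0.8 | 0.90 | 797 | 76% |

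As a gain in effective sample size, 1/0.65, 1/0.75 and 1/0.85 are 1.54, 1.33 and 1.18, that is 54%, 33% and 18%. With equal SDs, the change-score variance 2(1 − rho)·s² exceeds the follow-up variance s² when rho is below 0.5. In that range, change is less precise than ignoring baseline.

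**Unequal SDs (assumed s2 = 1.5·s1).** With s1 = 1, the change-score variance is 3.25 − 3·rho and the ANCOVA variance is 2.25·(1 − rho²).

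- rho 0.3: 2.350 v 2.0475, gain 15%
- rho 0.5: 1.750 v 1.6875, gain 4%
- rho 0.7: 1.150 v 1.1475, gain 0.2%

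The size of the gain therefore depends on the SD ratio as well as on rho.

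**Respiratory: what each contrast tests.** Take a constructed example with 443 per arm:

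- Baseline: 150 v 176 with the symptom. The difference is 26/443 = 5.87 points, pooled proportion 326/886 = 0.368, z = 1.81, p = 0.070.
- 12 months: 100 v 126. The difference is again 5.87 points, pooled proportion 226/886 = 0.255, z = 2.00, p = 0.045.

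Only the 12-month test falls below 0.05, yet the number affected fell by exactly 50 in each arm.

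**Respiratory: precision.** This was simulated with 1,000 replicates and 443 per arm. All rates are assumed: baseline prevalence 45% and conditional odds ratio 0.65. The 12-month control-arm risks with and without the symptom at baseline were 0.50 and 0.15 (moderate persistence) or 0.60 and 0.10 (strong persistence).

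| | 12-month chi-squared | logistic with baseline symptom |
|---|---|---|
| power, moderate | 0.71 | 0.77 |
| power, strong | 0.57 | 0.68 |
| type I error | 0.047 and 0.049 | 0.048 and 0.048 |

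At 350 per arm, power was 0.59 v 0.65 and 0.48 v 0.59. Both methods hold their error rate, and adjustment gains some power.

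**The case against.** The case for leaving the text alone is reasonable, and much of it stands.

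- A change score does use the baseline value. In the whole randomised sample it gives an unbiased comparison, and the SAP text and Tables 10 and 11 agree that change is the outcome. A reader might infer that baseline data are discarded or that the withdrawal analysis is biased; the SAP supports neither. The point is one of efficiency.
- The ratio (1 + rho)/2 needs equal SDs. At an SD ratio of 1.5 the gain nearly vanishes for rho of 0.5 or more. The 18% to 54% range is therefore illustrative and cannot be claimed for this trial.
- A reader might infer two separate chi-squared tests, one at baseline and one at 12 months. The sentence allows that reading, but Table 6 has room for only one P-value. What can be said is that the contrast is not fixed.
- A 12-month chi-squared test is a valid randomised comparison, and Table 6 prints baseline frequencies beside it, so an imbalance would be visible. It would be too strong to say that a chance imbalance will be taken for a treatment effect. The example above is constructed to show what the test measures.
- The withdrawal argument does not carry over to urges. They are analysed as follow-up scores, and no baseline urge rating is shown.

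Two things remain. Adjustment for a value already collected cannot lose precision in large samples, and the SAP already adjusts costs and QALYs this way. The single respiratory estimate also has no stated definition.

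**Conclusion.** The point holds as a minor, free improvement. For withdrawal, ANOVA on change is valid in the whole randomised sample but at best equals ANCOVA in precision. With equal SDs and rho from 0.2 to 0.8 it has the precision of about 60% to 90% of the sample. With a follow-up SD 1.5 times the baseline SD, the loss is small or negligible for rho of 0.5 or more. Correlation and SDs are assumptions throughout. The statement of validity does not extend to the abstainers-only analysis, whose sample is selected after randomisation; baseline adjustment would not cure that selection.

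For respiratory symptoms, the heading and Table 6 say change, the definition says status, and the contrast behind the one P-value and odds ratio is not fixed. A 12-month test ignores baseline status, and a baseline test between randomised arms tells the reader nothing useful. The power loss of roughly 6 to 11 percentage points rests on assumed symptom rates.

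Withdrawal is a listed secondary outcome. Respiratory change is in neither the list of objectives nor the list of outcome measures. The primary analysis and conclusion are unaffected.

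**What to change.** - **Withdrawal:** fit a linear model of the 1-week and of the 4-week withdrawal score on arm, baseline score and site. Report the adjusted mean difference with its 95% CI. Mean change by arm can stay in Tables 10 and 11 as description.
- **Respiratory:** for each symptom, regress 12-month status on arm, baseline status and site, using a log-binomial or logistic model. Name that single adjusted estimate and its P-value in Table 6. Choose the scale in advance: the general analysis principles call for a risk ratio, while the Table 6 shell shows an odds ratio. Keep the baseline frequencies as description without a test, and word the heading to match the estimate.
- **Urges:** leave the analysis as it is unless a baseline urge rating exists. If one does, adjust for it in the same way.

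The cost is a few lines of SAP text and a change to the table shells. The baseline and follow-up data are already in the collection schedule, and no change to sample size or conduct is needed.

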
Reason for stopping allocated product use in those not using it in the initial 4 weeks, N (%)
 
Cost Did not like the taste Adverse reaction Not satisfying Difficult to use Embarrassing to use Difficult to obtain them Smoking normal cigarettes now To quit nicotine Other reason
				

Any use of other products (including single use), N (%)
 
Varenicline Bupropion
				

^a Includes those who completed and part completed sessions over the telephone

Table 3 – Choice of product

Type of NRT selected, N (%) Using combination, N (%)
		

Switched to different NRT product in first 4 weeks N (%)
		

Type of EC used (cartridge based or refillable), N (%) 1 week post quit 4 weeks post quit 24 weeks post quit 52 weeks post quit
		

Switched to different EC in first 4 weeks N (%)
		

E-liquid used
		

Nicotine strength – mean (SD) 1 week post quit 4 weeks post quit 24 weeks post quit 52 weeks post quit
		

Flavours, N (%) 1 week post quit 4 weeks post quit 24 weeks post quit 52 weeks post quit
	
Tobacco Fruit Menthol/mint Tobacco menthol Vanilla Chocolate, dessert. Sweet or candy flavor No flavor Coffee Alcoholic drink Energy or soft drink Other Don't know
	

Given additional e-liquid at 2 weeks post-TQD, N (%) Purchased additional e-liquid at 2 weeks post-TQD, N (%)
		

Table 4 – Helpfulness, taste, and satisfaction of product

Rating	EC (n=...)	NRT (n=...)	P value	Mean difference (95% CI)
Helpfulness ^a , mean (SD) 1 week post quit 4 weeks post quit				
Taste compared to normal cigarettes, mean (SD) 1 week post quit 4 weeks post quit				
Satisfaction compared to normal cigarettes, mean (SD) 1 week post quit 4 weeks post quit				

^aWhere 2 NRT products were used and rated, the average rating of the two was taken.

Table 5 – Results for primary and secondary outcomes – unadjusted, using chi-square test; adjusted, using binomial regression

	NRT (n=...)	EC (n=...)	Unadjusted Relative Risk (95% CI)	Unadjusted P-value	Adjusted Relative Risk (95% CI)	Adjusted P-value
Primary outcome						
CO validated sustained abstinence at 52 weeks post TQD, N (%)						
Secondary Outcomes						
CO validated sustained abstinence between 24 and 52 weeks post TQD, N (%)						
CO validated sustained abstinence at 4 weeks post TQD, N (%)						
Sustained abstinence at 24 weeks post TQD, N (%)						
7-day point prevalence at 4 weeks post TQD, N (%)						
7-day point prevalence at 24 weeks post TQD, N (%)						

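### The SAP compares reasons for stopping product use as mean ratings by ANOVA, but its own Table 2 shows ten unordered categories with no score

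*SAP*

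**What the plan says.** The SAP (Analysis of secondary outcomes, Treatment ratings) sets one rule for four items: "Differences in mean ratings of treatment effects (product helpfulness, taste, satisfaction and reasons for stopping product use". The test is fixed in the same sentence: "satisfaction and reasons for stopping product use) between groups will be examined using ANOVA", with the alternative "or non-parametric tests where normality cannot be assumed) at 1 and 4 weeks post quit". The heading of that paragraph also names reasons for stopping.

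Other parts of the SAP describe the same variable differently:

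- Table 2 has a row block headed "Reason for stopping allocated product use in those not using it in the initial 4 weeks, N" (%). Its entries are "Cost Did not like the taste Adverse reaction Not satisfying Difficult to use Embarrassing to use Difficult to obtain them", then "Smoking normal cigarettes now To quit nicotine Other reason". That makes ten reasons, with no order among them.
- The table of mean ratings is "Table 4 – Helpfulness, taste, and satisfaction of product". It has no row for reasons for stopping.
- Appendix 3, item 9 gives a scale for each of three ratings, for example "Ratings of helpfulness on the following scale: not at all, slightly, somewhat, very, extremely". It gives none for reasons for stopping.

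**The concern.** A mean needs numbers whose spacing means something, and a rank test needs at least an order. A list running from cost to some other reason has neither. Following the sentence literally, the analyst must number the reasons and compare the average number between arms. That average says nothing about why people stopped, and the p-value depends on a numbering that the SAP does not set down.

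Why participants give up e-cigarettes or NRT helps a reader interpret product use in each arm. As the plan stands, the analyst must either run a test with no meaning for this variable or depart from the written plan.

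**Working it through.** The SAP states no sample size or power for this comparison, so there is no figure to reproduce. The check has two parts.

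**1. Type of variable against test**

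| Item | Scale in Appendix 3, item 9 | Summary in table shell | Test in text |
|---|---|---|---|
| Helpfulness, taste, satisfaction | Five ordered points | Mean (SD), Table 4 | ANOVA or non-parametric |
| Reasons for stopping | None | N (%), Table 2 | ANOVA or non-parametric |
| Adverse reactions (for comparison) | Yes/no | % (N), Table 7 | Chi-squared |

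The second row is the mismatch. The third shows that the SAP already uses a suitable test for categorical data in the same part of the document.

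**2. Dependence on the numbering (assumed data)**

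Assume 100 stoppers per arm, one reason each, with counts in Table 2 order:

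- NRT: 5, 15, 12, 18, 6, 4, 5, 20, 8, 7
- EC: 12, 10, 10, 12, 14, 6, 10, 14, 5, 7

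*Chi-squared.* With equal arm sizes, X² = Σ (NRT − EC)² / (NRT + EC) = 2.88 + 1.00 + 0.18 + 1.20 + 3.20 + 0.40 + 1.67 + 1.06 + 0.69 + 0 = 12.28 on 9 df, p = 0.198. No codes enter the formula.

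*ANOVA, codes 1 to 10 in listed order.* Mean codes are 534/100 = 5.34 (NRT) and 513/100 = 5.13 (EC), with SDs 2.80 and 2.77. F = 0.21² / [(2.80² + 2.77²)/100] = 0.28, p = 0.59. Mann-Whitney gives p = 0.61.

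*ANOVA, another numbering of the same data.* In Table 2 order, give the reasons codes 9, 3, 5, 1, 10, 7, 8, 2, 4, 6. Mean codes become 4.10 and 5.52, with SDs 2.76 and 3.18. F = 1.42² / [(2.76² + 3.18²)/100] = 11.4, p = 0.0009. Mann-Whitney gives p = 0.002. This numbering was chosen to show the extreme.

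*Random numberings.* Over 5000 random numberings, the ANOVA p-value ranged from 0.001 to 1.00 and about 10% fell below 0.05. Mann-Whitney ranged from 0.002 to 1.00, so a rank-based fallback has the same fault.

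**3. Power and false positives (assumed shares, 150 stoppers per arm, codes in listed order)**

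- *Shift A:* cost 12% v 2%, taste 12% v 22%, adverse reaction 10% v 18%, remainder spread evenly over the other seven reasons. Mean codes are 0.12 + 0.24 + 0.30 + 49 × 0.66/7 = 5.28 and 0.02 + 0.44 + 0.54 + 49 × 0.58/7 = 5.06. The shifts nearly cancel in the mean. Simulated power is about 91 to 93% for chi-squared and 9 to 10% for ANOVA.
- *Shift B:* cost 20% v 8%, smoking normal cigarettes now 20% v 32%, the other eight at 7.5% each. Mean codes are 0.20 + 1.60 + 3.45 = 5.25 and 0.08 + 2.56 + 3.45 = 6.09. Simulated power is about two thirds for chi-squared and about 70% for ANOVA.
- *No difference between arms:* ANOVA on fixed codes rejected in 4.6 to 5.7% of simulated trials, close to the nominal 5%.

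**The case against.** The strongest reply is that this is a slip of wording which the rest of the SAP already corrects. The follow-up data list names the ratings and the reasons for stopping as separate entries, Table 4 and Appendix 3 leave reasons out of the ratings, and Table 2 counts them. No code and no mean for reasons appears anywhere, so a sensible analyst would tabulate percentages. This stands as a reading of what was probably intended. It does not remove the written rule, which names the item twice and assigns it a method.

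A second reply is that the non-parametric alternative could cover chi-squared. The clause names no test and is triggered by non-normality, not by lack of order, so it does not clearly do so.

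A third is that ANOVA does little harm if each reason is treated as yes or no. This is true: for the first reason in the assumed data, ANOVA gives p = 0.077 and chi-squared 0.076. But the SAP does not say the reasons will be handled that way, and a mean rating suggests otherwise.

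Three stronger readings are tempting and are not supported:

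- A reader might infer that the test produces false positives. Once a numbering is fixed, the error rate stays near 5%. The risk lies in the numbering being left open.
- A reader might take the contrast of about 93% against 9% power as the cost of the error. It belongs to one assumed pattern with shifts in adjacent codes; shift B shows no loss. With shift A and 50 stoppers per arm, chi-squared itself has only about one third power.
- A reader might take the mean-difference column of Table 2 as proof that reasons will be averaged. That heading spans a mixed table with other percentage rows, so it is weak evidence.

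**Conclusion.** The point holds as an error in the stated method. The Treatment ratings sentence applies a comparison of means to a variable that the SAP's own table shows as nominal, and nothing else in the SAP supplies a score.

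The consequence depends on the reasons being analysed as one coded variable. In that case the result cannot be interpreted, varies with an unspecified numbering, and may have low power. How low cannot be said from the SAP, which gives neither the number of stoppers nor the shares of reasons. The illustrations also assume one reason per person. The case report form that would settle this is cited in Appendix 1 but is not part of the text at hand.

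Severity is low. The item is descriptive, sits in the adherence table, and concerns a subset defined after randomisation. The listed secondary outcome on treatment ratings gives satisfaction and helpfulness as its examples, not reasons for stopping. The primary outcome is unaffected.

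**What to change.** - Delete reasons for stopping product use from the ANOVA sentence. Keep ANOVA or non-parametric tests for helpfulness, taste and satisfaction.
- State that N (%) for each reason will be reported by arm among those who stopped.
- If only one reason can be given, compare arms by a single chi-squared or Fisher's exact test across the reasons. If several can be given, compare each reason as yes/no, with a risk difference or ratio and 95% CI.
- Mark the mean-difference column of Table 2 N/A for these rows, as the shell already does for another block.

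The cost is a short change to the text and to one table shell. No new data are needed.
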